9 STUDY MEDICATION

9.1 EXTENT OF EXPOSURE

Exposure to study medication will be summarized by treatment group in terms of treatment duration in weeks, which is calculated using the following formula: (the date of last medication taken - the date of first dose taken +1)/7.

Total weekly study drug exposure is defined as the total prescribed dose (in mg and mg/kg for Roxadustat and IU and IU/kg for EPO) of study drug administered within the week (windowed by 7-day period from Day 1).

Duration of exposure, weekly exposure and total study drug exposure will be tabulated by treatment group for the safety population.

Per administration amount and administration frequency will also be tabulated by treatment group for the safety population and PPS population.

Patient-Exposure-Year (PEY) is defined as (Last Dose Date – First Dose Date + 1)/365.25.

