11 EFFICACY ANALYSES

Efficacy analysis will be conducted on the ITT and FAS for US (FDA) submission and analysis for non-inferiority on the PPS population and analysis for superiority on FAS population for EU regulatory submission.

The **Efficacy Emergent Period** is defined as the evaluation period from the Analysis date of first dose intake up to 7 days after the Last Dose of study drug or EOT Visit, whichever occurs first. This period will be used as reference period for the time to event analyses related to efficacy endpoints, unless specified otherwise.

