11.3.2 Hospitalizations (including skilled nursing facility)

Hospitalizations are collected in the Hospitalization Records Form of the eCRF. For each subject, an entry will be recorded for each hospitalization. The days of hospitalization will be calculated as the sum of all hospitalizations durations in days (Date of discharge – Date of Admission + 1). In case of missing dates, the hospitalization duration will be assumed to be 5 days.

Only hospitalizations with admission dates that occur during the treatment period and up to 7 days after the last study medication date will be taken into account.

The following hospitalization-related data will be analyzed and compared between the 2 treatment groups:

- Time to first hospitalization up to Week 52- Proportion of subjects hospitalized. Time to first hospitalization or skilled nursing facility up to Week 52.
- Number of days of hospitalizations
- Number of days of medical-facility
- Number of days of hospitalizations per patient-exposure year (PEY).
- Number of days in hospital or skilled nursing facility per patient-year exposure (PEY)
- Number of days of medical-facility per subject-exposure year (PEY).

- Number of days on treatment out of hospital and skilled nursing facility up to Week 52, 7 days after Last Dose. The days will be compared between the 2 treatment groups using ANCOVA model with baseline Hb and the baseline stratification factors.

Note: Elective procedures may be excluded from analyses by using only hospitalization due to AE.

The time to hospitalization event will be compared between the two treatment groups using cox model including baseline stratification factors. The proportion of subjects hospitalized will be compared between the 2 treatment groups using logistic regression model and stratified by the baseline stratification factors. The mean number of days of hospitalization will be analyzed and compared between the 2 treatment groups using the Mantel-Haenszel mean score test adjusting for stratification factors.

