11.3.4 Rescue Therapy Use

11.3.4.1 Blood Transfusion

For a subject receiving RBC transfusion, the Time at Risk (time up to first RBC transfusion) will be calculated (in years) as:

$$(\text{First RBCtransfusion date} - \text{First dose date of study medication} + 1) / 365.25$$

For a subject not receiving transfusion, the Time at Risk (time until they get censored) is calculated as:

$$(\text{Date of last study medication} - \text{First dose date of study medication} + 1) / 365.25$$

The blood transfusion form of the eCRF in the cumulative visit will be used to derive the number of RBC packs. The number of RBC units is collected in this form. For transfusions where the number of units is not given but the volume transfused is given, the number of units will be estimated by dividing the volume transfused by 250 mL (for transfusion of packed cells) or by dividing the volume transfused by 500 mL (for transfusion of whole blood).

The total number of RBC units/packs during the treatment period is calculated for each subject by the sum of the transfused units between the Analysis Date of First Dose and up to the Analysis Date of Last Dose. The following 2 endpoints will be analyzed:

- Proportion of subjects who receive RBC transfusions. The proportion of subjects who received RBC transfusion will be compared between the 2 treatments using logistic regression model adjusting for baseline stratification factors.
- Number of RBC packs per patient-month exposure to study medication. The mean number of RBC packs will be compared between the 2 treatment groups using ANCOVA model with baseline hemoglobin as covariate and treatment and stratification factors as fixed effect.

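### Hospital, skilled-nursing and medical-facility days per patient-exposure-year count post-treatment days in the numerator that have no matching time in the denominator

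*SAP*

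**What the plan says.** **Numerator.** SAP 11.3.2 admits a stay to the analysis on its admission date: "Only hospitalizations with admission dates that occur during the treatment period and up to 7 days after the last study medication date" count. On length, it states: "The days of hospitalization will be calculated as the sum of all hospitalizations durations in days", each duration being discharge date minus admission date plus 1. Nothing cuts a stay at the end of the 7-day window. For incomplete records the rule is: "In case of missing dates, the hospitalization duration will be assumed to be 5 days".

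**Denominator.** SAP 9.1 states: "Patient-Exposure-Year (PEY) is defined as (Last Dose Date – First Dose Date + 1)/365.25". No other definition of PEY appears, and none adds 7 days.

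**Endpoints affected.** SAP 11.3.2 lists days per PEY for hospitalization, for hospital or skilled nursing facility, and for medical facility. SAP 4.4 lists them as additional evaluations of efficacy, and protocol 7.3 also lists hospital days per PEY. The SAP does not say whether the rate is total days over total exposure or an average of subject ratios. The only test it names for days, a Mantel-Haenszel mean score test, is on the mean number of days, not on a rate.

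**Transfusion.** SAP 11.3.4.1 measures time to the first RBC transfusion without naming a latest eligible date. It then reads: "For a subject not receiving transfusion, the Time at Risk (time until they get censored) is calculated as" last study medication date minus first dose date plus 1. RBC units are summed only to the last dose. SAP 11 sets a default period for efficacy time-to-event analyses ending "up to 7 days after the Last Dose of study drug or EOT Visit, whichever occurs first", unless specified otherwise.

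**The concern.** A rate per unit of exposure needs events and exposure drawn from the same interval. Here the numerator can run past the denominator by the gap between last dose and admission (up to 7 days) plus the whole of the stay. A subject whose drug stops at a hospital admission contributes every day of that stay, and almost none of those days enters the exposure.

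The mismatch occurs only where treatment ends, so it weighs more on an arm with more discontinuations, or with more discontinuations around hospital admission. The trial is open-label, and protocol 3.5.3.3 foresees that roxadustat may not be allowed or available in hospital. For a subject who never resumes, the last roxadustat dose may then fall at or before admission. That is an inference, but it is a reason not to assume that the effect is equal in the two arms. At stake is the between-arm comparison of hospital burden per year.

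**Working it through.** The documents report no hospital-day rate, so there is no figure of theirs to reproduce. The check applies the SAP formulas directly.

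**Subject level.** With exposure of E days and a stay of L days:

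- SAP rate = L / (E/365.25) = 365.25 × L/E, which exceeds 365.25 whenever L > E.
- Matched rate = 365.25 × (hospital days up to last dose + 7) / (E + 7). If admission is g days after last dose, the days kept are min(L, 7 − g + 1).

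| E | g | L | SAP rate | Days kept | Matched rate |
|---|---|---|---|---|---|
| 7 | 3 | 10 | 521.8 | 5 | 130.4 |
| 14 | 3 | 20 | 521.8 | 5 | 87.0 |
| 28 | 5 | 30 | 391.3 | 3 | 31.3 |
| 365 | 5 | 30 | 30.0 | 3 | 2.9 |

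The untruncated stay is the larger cause. A 30-day stay starting on the day of the last dose, after 20 days of exposure, gives 365.25 × 30/20 = 547.9 without using the 7-day window at all. Adding 7 days to the denominator alone does not cure it: for the second row, 365.25 × 20/21 = 347.9, and a longer stay would pass 365.

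**Arm level, simulated.** All inputs are assumptions: 520 subjects per arm, 1.5 admissions per year, mean stay 7 days on drug and 10 days after stopping, 5 to 40% of early stoppers admitted within 7 days of last dose, discontinuation hazard 0.2 to 0.4 per year, 2-year maximum.

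| Form of rate | SAP rule | Matched window | Excess |
|---|---|---|---|
| Pooled (total days / total PEY) | 10.7 to 12.2 | 10.3 to 10.9 | about 4 to 12% |
| Mean of subject ratios | 12.0 to 21.3 | 10.4 to 12.6 | about 16 to 69% |

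About 0.4 to 2.2 subjects per arm exceed 365.25 days per year under the SAP rule. Part of the pooled excess, about 1.5 percentage points, comes from simulated stays that overlap: the SAP sum counts those days twice and the matched version does not. With distinct days in both, the excess is about 3 to 11%.

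**How much of a between-arm difference the mismatch explains.** Assume 10 on-drug hospital days per PEY, mean exposure 1.2 years, and 10 post-dose hospital days per affected subject.

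- SAP rule: (10 × 1.2 + 10s)/1.2. With s = 10% this is 10.83; with s = 20% it is 11.67; ratio 1.077.
- Matched window, keeping 7 of the 10 days and ignoring other subjects' days in the added week: (12 + 7s)/(1.2 + 7/365.25). With s = 10% this is 12.7/1.219 = 10.42; with s = 20% it is 13.4/1.219 = 10.99; ratio 1.055.

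Aligning the windows moves the ratio from 1.077 to 1.055, not to 1.

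**Transfusion.** Assume an on-drug rate of 0.12 per year in both arms, discontinuation at 0.4 versus 0.2 per year, and 1 to 10% of stoppers transfused within 7 days. Counting events to last dose + 7 days but censoring at last dose gives crude rate ratios of 1.016 to 1.143. Adding the missing person-time gives 1.013 to 1.139. The mismatch itself is therefore worth about 0.003 to 0.004; the rest comes from counting the extra week of events.

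**The case against.** Counting the full length of a stay that began on treatment is a defensible measure of burden, and truncation discards real days. That stands for a count of days, which is why full-stay totals should still be shown. It does not justify dividing those days by time that ends earlier.

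Four stronger readings are tempting, and the documents do not support them:

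- **Reported rates above 365 days per year.** This happens only in subject-level ratios, which the SAP never says it will average. A pooled arm rate comes nowhere near that value.
- **Negative medical-facility-free days.** SAP 4.4 names the endpoint but no section gives a formula for it, so nothing can be said about its sign.
- **Matching the windows removes the between-arm excess.** It does not. In the illustration above, 5.5 of the 7.7 points remain, because the arm with more treatment-ending stays really does have more hospital days.
- **A compromised fixed-sequence test.** Time to first RBC transfusion is in SAP Table 5 with a margin of 1.8, but it is defined as occurring during the treatment, and 11.3.4.1 ends both censoring and unit counts at last dose. The default period in SAP 11 yields to specific rules and can end earlier, at the EOT visit. A consistent reading, with everything stopping at last dose, is available. What remains is that no cut-off is written for the event itself.

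Materiality is also limited: the per-PEY endpoints lie outside Table 5, and SAP 5.3 makes no multiplicity adjustment for them.

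**Conclusion.** The mismatch is real on the text. As written, the three facility-day rates per PEY include post-treatment days without matching person-time, and are inflated as a result. The inflation is modest if rates are pooled, about 4 to 12% under the assumed admission, stay and discontinuation inputs. It is larger if subject ratios are averaged, a choice that the SAP leaves open. Because it arises at discontinuation it need not cancel between arms; its size and direction in this trial cannot be known from the documents. It affects additional efficacy endpoints only. The transfusion point is one of consistency, with a negligible expected effect. The correction is worth making because it is cheap and the definitions cannot be defended as a rate.

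**What to change.** In SAP 11.3.2, for the per-PEY endpoints:

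1. Count distinct calendar days in the facility from first dose to last dose + 7 days, truncated at death, and at Week 52 where an endpoint is limited to Week 52.
2. Apply the same truncation to stays given the imputed 5-day length.
3. Use that same window, in years, as the denominator in place of the PEY of SAP 9.1.
4. State that the rate is total days over total person-time in each arm.
5. If wanted, show total days of full stays separately, as a count and not a rate.

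In SAP 11.3.4.1, name one cut-off, either last dose or the end of the Efficacy Emergent Period, and apply it to first-transfusion events, censoring and RBC units.

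The cost is SAP wording and programming. The plan already uses admission, discharge, transfusion and dose dates, and early stoppers are followed for hospitalization until study closure (protocol 6.1.2.6). Reported rates would be somewhat lower.

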11.3.3 Missed Dialysis Sessions

Missed dialysis sessions are collected in the Dialysis Modality Form of the eCRF. For each subject, an entry will be recorded for missing dialysis. The number of missing dialysis will be summarized by treatment group.

The following missing dialysis-related data will be analyzed and compared between the 2 treatment groups:

- Occurrence (number) of missed dialysis sessions. The number of missed dialysis sessions for each subject will be collected. The mean number of missed dialysis sessions will be analyzed and compared between the 2 treatment groups using Mantel-Haenszel mean score test adjusting for stratification factors.
- Proportion of subjects with missed dialysis sessions. The proportion of subjects missed dialysis sessions will be compared between the 2 treatment groups using CMH model and stratified by the baseline stratification factors.
- Number of days of missed dialysis sessions per patient-exposure year (PEY). The number of days of missed dialysis sessions for each subject will be calculated (# of missed dialysis/weekly prescribed dialysis frequency* 7), where weekly prescribed dialysis is TIW in this study. The mean number of days of missed dialysis sessions will be analyzed and compared between the 2 treatment groups using the Mantel-Haenszel mean score test adjusting for stratification factors.

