#### 3.5.2.2 Active Control Arm (Epoetin alfa)

Subjects on HD will initiate intravenous (IV) treatment according to the epoetin alfa US Package Insert (USPI) or Summary of Product Characteristics (SmPC).

For subjects on HHD or PD, epoetin alfa will be administered according to the epoetin USPI, or SmPC or local standard-of-care.

For countries using prefilled syringes, the initial epoetin alfa dose and dose adjustments should be approximated to the closest weekly dose.

**Table 1** Initial Study Drug Dosing

Study Drug (Dose Frequency)	Low Weight (≤ 70 kg)	High Weight (> 70 to 160 kg)
Roxadustat (TIW)	70 mg	100 mg
Active Control HD (TIW)	IV dosing according to epoetin alfa Package Insert or SmPC.	
Active Control PD/HHD	Epoetin alfa should be administered according to the epoetin alfa Package Insert or SmPC or local standard of care.	

Abbreviations: HD = hemodialysis; HHD= home-hemodialysis; PD = peritoneal dialysis; SmPC = summary of product characteristics; TIW = three times a week.

Note: Weight in HD subjects = subject's dry weight.

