## 4 ELIGIBILITY CRITERIA

### 4.1 Inclusion Criteria

1. Age  $\geq$  18 years.
2. Subject has been informed of the investigational nature of this study and has given written informed consent in accordance with institutional, local, and national guidelines.
3. Receiving HD or PD for ESRD for a minimum of 2 weeks and a maximum of 4 months, prior to randomization.
4. Hemodialysis access consisting of an arteriovenous (AV) fistula, AV graft, or tunneled (permanent) catheter; or PD catheter in use.
5. Mean of the two most recent predialysis Hb values during the Screening Period, obtained at least 2 days apart, must be  $\leq$  10.0 g/dL, with a difference of  $\leq$  1.3 g/dL between the highest and the lowest values. The last Hb value must be drawn within 10 days prior to randomization.
6. Ferritin  $\geq$  100 ng/mL ( $\geq$  220 pmol/L); subjects with ferritin level  $<$  100 ng/mL ( $<$  220 pmol/L) during screening, qualify after receiving iron supplement (per local standard of care), without the need to retest ferritin prior to randomization.
7. Transferrin saturation  $\geq$  20%; subjects with TSAT level  $<$  20% during screening, qualify after receiving iron supplement (per local standard of care), without the need to retest TSAT prior to randomization.
8. Serum folate level, performed within 8 weeks prior to randomization  $\geq$  lower limit of normal (LLN); subjects with serum folate level  $<$  LLN during screening, qualify after receiving folate supplement (per local standard of care), without the need to retest folate prior to randomization.
9. Serum vitamin B12 level, performed within 8 weeks prior to randomization  $\geq$  LLN; subjects with vitamin B12 level  $<$  LLN during screening, qualify after receiving B12 supplement (per local standard of care), without the need to retest B12 prior to randomization.
10. Alanine aminotransferase (ALT) or aspartate aminotransferase (AST)  $\leq$  3 x upper limit of normal (ULN), and total bilirubin (Tbili)  $\leq$  1.5 x ULN.
11. Body weight up to 160 kg (HD subjects: dry weight).

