4.4 ADDITIONAL EVALUATION OF EFFICACY

The additional efficacy evaluations in this study are:

- **Hb Correction and Maintenance:**
 - Hemoglobin maintenance: Mean change from baseline in Hb averaged over 8 weeks of treatment at Weeks 28 to 36, without rescue therapy within 6 weeks prior to and during this 8-week evaluation period.
 - Hemoglobin long-term Maintenance: Mean change in Hb averaged over 8 weeks of treatment at Weeks 44-52 without rescue therapy within 6 weeks prior to and during this 8-week evaluation period.
 - Mean change from baseline in Hb averaged over the 96 to 104 weeks of treatment, without rescue therapy within 6 weeks prior to and during this 8-week evaluation period.
 - Change from baseline in Hb at each of the selected post-dosing time points.
 - Proportion of subjects with Hb ≥ 10 g/dL averaged over Weeks 28-36, without rescue therapy within 6 weeks prior to and during this 8-week evaluation period.
 - Proportion of subjects with mean Hb < 9 g/dL, 9- <10 , 10- <11 , 11- <12 , 12- <13 , ≥ 13 g/dL during Weeks 28-36
 - Proportion of patient exposure (PEY) with Hb < 9 g/dL, 9- <10 , 10- <11 , 11- <12 , 12- <13 , ≥ 13 g/dL during weeks 28 to 52
- **Hospitalizations:**
 - Time to first hospitalization (% of subjects) up to Week 52.
 - Time to first hospitalization or skilled nursing facility (% of subjects) up to Week 52
 - Number of days of hospitalizations per patient-exposure year (PEY).
 - Number of days of hospital or skilled nursing facility per PEY
 - Number of medical-facility free days (hospital, skilled nursing facility, emergency room, or overnight observation) per PEY
 - Number of days on treatment out of hospital and skilled nursing facility up to Week 52, 7 days after Last Dose.
- **Missed dialysis sessions up to Week 52**
 - Occurrence (number) of missed dialysis sessions
 - Proportion of subjects with missed dialysis sessions
 - Number of days of missed dialysis sessions per patient-exposure year (PEY)

- **Rescue Therapy Use up to Week 52:**
 - Proportion of subjects who receive RBC transfusions.
 - Number of RBC packs per patient-month exposure to study medication.
 - Roxadustat subjects: The proportion of subjects requiring ESA rescue therapy (ATC code: B03XA01)
- **Changes in Cholesterol Levels:**
 - Change at each of the protocol specified treatment time points in:
 - total cholesterol,
 - low-density lipoprotein (LDL)/high-density lipoprotein (HDL) ratio,
 - non-HDL cholesterol.

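### SAP 11.3.3 converts missed dialysis sessions to days at three sessions a week for every subject, so the days figure is wrong for anyone prescribed a different frequency

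*SAP*

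**What the plan says.** SAP 4.4 lists three missed-dialysis measures up to Week 52 among the additional efficacy evaluations: "Occurrence (number) of missed dialysis sessions", "Proportion of subjects with missed dialysis sessions", and "Number of days of missed dialysis sessions per patient-exposure year (PEY").

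SAP 11.3.3 names the data source ("Missed dialysis sessions are collected in the Dialysis Modality Form of the eCRF") and derives the third measure as the number "of missed dialysis/weekly prescribed dialysis frequency* 7". It then replaces the frequency term with one value for the whole trial: "where weekly prescribed dialysis is TIW in this study". It makes no exception by modality. The mean number of sessions and the mean number of days are both compared with the Mantel-Haenszel mean score test, adjusted for the stratification factors.

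Protocol 4.1, criterion 3, admits both modalities: "Receiving HD or PD for ESRD for a minimum of 2 weeks and a maximum of 4 months, prior to randomization". Protocol 3.5.2.2 shows that home-haemodialysis subjects are expected as well: "For subjects on HHD or PD, epoetin alfa will be administered according to the epoetin USPI, or SmPC or local standard-of-care".

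**The concern.** The formula as first written is sensible: one missed session out of f a week stands for 7/f days. The clause that follows removes the only part that depends on the subject. It is worded as a fact about the study, but no section of either document prescribes dialysis three times a week. Elsewhere in the documents, three times weekly is the dosing frequency of roxadustat or of epoetin alfa, not a dialysis schedule.

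Two things are at stake. The first is the absolute level of days missed per patient-exposure year, which a reader would take at face value. The second is whether the days measure tells the reader anything that the session count does not.

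**Working it through.** The SAP states no numerical result for this measure, so there is no figure of its own to reproduce. The check is of the derivation.

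**Inputs.** The formula and the constant 3 come from SAP 11.3.3. Eligibility of PD subjects comes from Protocol 4.1, and the presence of HHD subjects from Protocol 3.5.2.2. No prescribed frequency is given for PD or HHD, so f is varied over an assumed range. The modality mix is not given either. The earlier incident-dialysis study in Protocol 1.4.2.2 had 12 PD subjects out of 60 (20%), so shares of 5% to 30% are used as an assumed range.

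**Step 1: error per missed session.** The SAP gives 7/3 = 2.33 days to everyone. With the subject's own frequency it is 7/f. The ratio of the two is (7/3)/(7/f) = f/3.

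| f (sessions a week, assumed) | Days per missed session, 7/f | SAP value divided by 7/f |
|---|---|---|
| 2 | 3.50 | 0.67 |
| 3 | 2.33 | 1.00 |
| 4 | 1.75 | 1.33 |
| 5 | 1.40 | 1.67 |
| 6 | 1.17 | 2.00 |
| 7 | 1.00 | 2.33 |

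Seven missed treatments on a daily schedule span 7 days; the SAP rule gives 7 × 7/3 = 16.3 days.

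**Step 2: effect on the overall mean.** Let a share s of subjects have frequency f and the rest have 3.

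- If everyone misses the same number of sessions, the overstatement is (7/3) / [(1 − s) × 7/3 + s × 7/f]. At s = 0.20 and f = 7 this is 2.333 / (1.867 + 0.200) = 1.13.
- If everyone misses the same fraction of sessions, it is (1 − s) + s × f/3. At s = 0.20 and f = 7 this is 0.80 + 0.467 = 1.27.
- Over s from 5% to 30% and f from 4 to 7, the overstatement runs from about 1% (s = 5%, f = 4, same sessions: 1.013) to 40% (s = 30%, f = 7, same fraction: 1.40).

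**Step 3: what the constant does to the test.** With f fixed at 3, each subject's days before division by exposure are exactly 7/3 times the session count. In the mean score statistic this multiplies both the squared numerator and the variance by (7/3)², which cancels. One simulated data set (600 subjects, four strata, 20% at f = 7) confirms it: the statistic was 0.031 for the count, 0.031 for days as the SAP derives them, and 0.575 for days using each subject's own frequency. The third value shows only that the measure becomes distinct once frequency varies. It says nothing about direction or size of a treatment effect.

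**The case against.** The strongest reply is that nothing shows how many subjects are affected. An HHD subject prescribed three sessions a week is converted correctly. The Dialysis Modality Form is not available for review, so missed PD treatments may not be recorded as sessions at all, in which case no PD days are inflated. All of this stands, and it limits the point to subjects whose prescribed frequency is not three. A reader might infer that the measure is wrong for every PD and HHD subject; the documents do not support that.

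A reader might also infer that, because modality is not a stratification factor, the constant distorts the comparison between arms. That does not follow either. The constant only rescales the count, so it adds no distortion that the count does not already carry. Allocation is randomised 1:1, so a modality imbalance is noise and not systematic bias. As an illustration, take 500 per arm (SAP 5.1 mentions approximately 1000 subjects), PD shares of 5% to 30%, daily PD, and the same fraction of sessions missed in each modality.

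- The standard error of the arm difference in PD share is √(2 × 0.05 × 0.95/500) = 1.4 percentage points at 5%, and √(2 × 0.30 × 0.70/500) = 2.9 at 30%.
- Mean SAP days are proportional to 1 + 4s/3. One standard error therefore moves them by (4/3 × 0.0138)/1.067 = 1.7% at the low end and (4/3 × 0.0290)/1.40 = 2.8% at the high end.

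The reach is also small. This is one of three missed-dialysis measures, outside the fixed sequence in SAP 11.2 (Table 5), and SAP 5.3 applies no multiplicity adjustment to it.

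What the reply does not remove is that the stated rule rests on a frequency neither document supports for a mixed-modality population.

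**Conclusion.** The derivation is wrong as written for any subject whose prescribed frequency is not three a week, by a factor f/3. It overstates days when f is above 3 and understates them when f is below 3. The size depends on assumed frequencies and an assumed modality mix; within the ranges used, the overall mean would be overstated by about 1% to 40%. The absolute figure for days per patient-exposure year is therefore unreliable, and the test on days duplicates the test on the count.

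No systematic between-arm bias is shown. The number of missed sessions, the proportion of subjects with missed sessions, and all primary and key secondary endpoints are unaffected. This is a minor correction, worth making because it is cheap.

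**What to change.** In SAP 11.3.3, delete the clause that fixes the frequency. Divide each missed session by that subject's own prescribed weekly frequency at the time of the miss, if the Dialysis Modality Form captures it. State how a missed PD treatment is counted.

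If the form does not hold prescribed frequency, restrict the days measure to in-centre haemodialysis subjects, write down three sessions a week as an assumption, and report PD and HHD subjects by count only. This fallback still requires that the data separate in-centre from home haemodialysis; the documents do not show the form's fields.

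The cost is a SAP sentence or two and one derivation. The downside of the fallback is a smaller analysis set for this one additional endpoint. Nothing here touches any subject's dialysis schedule or treatment.
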